#### Normal Ranges for Vital Signs

Vital Signs (unit)	Lower Limit	Upper Limit
Systolic BP (mmHg)	<90	>120
Diastolic BP (mmHg)	<60	>80
Pulse Rate (bpm)	<60	>100
Respiration Rate (bmp)	<12	>18
Body Temperature (F)	<98	>99.1

#### LABORATORY ASSESSMENTS

BLOOD CHEMISTRY ALAT (SGPT) ALBUMIN ALKALINE PHOSPHATASE ASAT (SGOT) UREA NITROGEN CALCIUM	HEMATOLOGY WITH % DIFFERENTIAL HEMATOCRIT HEMOGLOBIN WHITE CELL COUNT BASOPHILS EOSINOPHILS	BONE BIOMARKERS BONE CTx BONE BSAP HORMONES FOLLICLE STIMULATING HORMONE (FSH)
CALCIUM CARBON DIOXIDE (CO2) CHLORIDE	D2) EOSINOPHILS LYMPHOCYTES MONOCYTES	LUTEINIZING HORMONE (FSH) SEX HORMONE BINDING GLOBULIN (SHBG)

Page 9 of 15

CHOLESTEROL, TOTAL HDL LDL-CHOL CALCULATION CREATININE BILIRUBIN, DIRECT GLUCOSE LACTIC DEHYDROGENASE POTASSIUM SODIUM BILIRUBIN, TOTAL PROTEIN, TOTAL SERUM TRIGLYCERIDES	NEUTROPHIL, SEGS TOTAL NEUTROPHILS RED CELL COUNT PLATELET COUNT	ESTRADIOL ESTRONE COAGULATION FACTORS PROTEIN C ACTIVITY PROTEIN S ACTIVITY ANTITHROMBIN III ANTIGEN ACTIVATED PROTEIN C RESISTANCE (APCR)		
Formulas of Metric Conversion:				
• 1 inch = 2.54 cm				
• 1 lb = 0.4536 kg				
• $^{\circ}C = (^{\circ}F - 32)x5/9$				

#### 3.8 Change to Planned Protocol Analysis

Since the study was early terminated, many subjects did not have visit of End of Blinded Phase at week 52. The current nominal Visit of "Week 52" will include both "Week 52" and "End of Study" (EOS). No imputation will be done for the missing data.

Since the study was terminated early, a brief clinical study report will be planned for this study and will focus on the safety and PK/PD results, where PK/PD results of blind phase will be reported only. The baseline characters, safety data and PK/PD data will be reported in the study report.

However, mammographic efficacy data may be analyzed appropriately as ad-hoc analyses after carefully reviewed data. The results of ad-hoc analyses will be reported separately.

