# 1.3 Change in Study Conduct

The study was early terminated. Following careful consideration and review of the development program for BHR700 (4-Hydroxytamoxifen Gel, 4-OHT), it was determined that breast density reduction may not be the optimal surrogate marker to support drug development for a target indication of the reduction of the risk of breast cancer.

Planned analyses will be conducted using data available in the clinical database. The sample size of the study may no longer be powered due to the lower number of subjects and shorter duration of treatment for a large proportion of subjects due to the early termination of the study. Therefore, the

interpretation of the analysis results will be cautious. Moreover, the emphasis of the statistical analysis will be on descriptive statistics, rather than hypothesis testing.

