#### 2.2.2 Secondary Endpoints

- 1 The percentage reduction in breast density at Week 52 using two breast density measurement methods (Cumulus versus Volpara).
- 2 The percentage of women who underwent a change in BI-RADS category when comparing pre-and post-treatment measurements.
- 3 The percentage of women with a ± 10% absolute decrease in quantitative mammographic density (Cumulus) between baseline and 52 weeks,
- 4 Change in serum concentration of: cholesterol, triglycerides, high-density lipoprotein (HDL), and low-density lipoprotein (LDL).
- 5 Change in serum concentration of sex hormone binding globulin (SHBG).
- 6 Change in serum concentration of Protein C-activity, Protein S-activity, Antithrombin 111 antigen, and Activated Protein C resistance (APCR).
- 7 Change in serum concentration of select bone biomarkers CTx and BSAP.
- 8 Incidence and severity of AEs and laboratory values.
- 9 The menstrual cycle of premenopausal women.
- 10 Pharmacokinetic (PK) plasma concentration of the E and Z isomers of 4-OHT after 13, 26, 52, 78, and 104 weeks of application of 4 mL BHR-700 gel to the breasts.

The secondary endpoints are for both blind and open-label treatment phases.

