# 3. STATISTICAL METHODS

#### 3.1 General

All data will be analyzed using the Statistical Analysis System (SAS®; Version 9.2 or higher).

Safety and efficacy data will be summarized and presented by treatment group and time point in summary tables. Continuous variables will be presented by descriptive statistics: n, mean, standard deviation, median, minimum, and maximum. Categorical variables will be tabulated by frequency count and percentage.

When the actual treatment received by a subject is different from the randomized treatment assigned, the subject will be analyzed per the randomized treatment for the efficacy parameters (using the ITT population); while the subject will be analyzed per actual treatment that was taken for the safety parameters (using the safety population).

Where appropriate, all statistical tests will be two-sided hypothesis tests performed at the 5% level of significance for main effects and all confidence intervals will be two-sided 95% confidence intervals.

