#### 3.6 **Pharmacodynamic and Pharmacokinetic (PD/PK) Data**

- Bone biomarkers (CTx and BSAP) level and change from baseline will be summarized by visit and treatment group. Individual data listing will also be provided.
- Plasma concentration of study agent (4-OHT E&Z isomers) will be summarized by visit and treatment group. Individual data listing will also be provided.
- Hormones (FSH, Estradiol and Estrone) will be summarized by visit and treatment group. Individual data listing will also be provided.
- Coagulation parameters (Protein C Activity, Protein C antigen, Protein S antigen total, Protein S antigen free, Antithrombin III antigen, Activated protein C resistance) will be summarized by visit and treatment group. Individual data listing will be provided as well.

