# 4.1.3 Summary of PK/PD endpoints

- 20. Table [THR01a] Summary of Hormones Results (Blinded Phase) ITT Population
- 21. Table [TBB01a] Summary of Bone Biomarker Results (Blinded Phase) ITT Population
- 22. Table [TCP01a] Summary of Coagulation Parameters Results (Blinded Phase) ITT Population
- 23. Table [TPK01a] Summary of Plasma Concentration Results (Blinded Phase) ITT Population
- 24. Table [TEM01a] Summary of Endometrial Change (Blinded Phase) ITT Population (Only if data available)

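### SAP 3.8 files End of Study records under Week 52, so the only blinded-phase post-baseline summary of CTx and BSAP mixes different treatment durations

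*SAP*

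**What the plan says.** SAP 3.8 explains that, because the study stopped early, "many subjects did not have visit of End of Blinded Phase at week 52". It then gives the rule: "The current nominal Visit of 'Week 52' will include both 'Week 52' and 'End of Study' (EOS". The same section rules out imputation and makes safety and PK/PD the focus of the report. SAP 1.3 describes the exposure: "shorter duration of treatment for a large proportion of subjects due to the early termination of the study".

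The rule feeds tables laid out by time point. SAP 3.1 states: "Safety and efficacy data will be summarized and presented by treatment group and time point in summary tables". SAP 3.6 is more specific for the markers: "Bone biomarkers (CTx and BSAP) level and change from baseline will be summarized by visit and treatment group", and "Hormones (FSH, Estradiol and Estrone) will be summarized by visit and treatment group".

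SAP 2.2.2 lists as a secondary endpoint: "Change in serum concentration of select bone biomarkers CTx and BSAP". The planned output in SAP 4.1.3 is "Table [TBB01a] Summary of Bone Biomarker Results (Blinded Phase) ITT Population".

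Protocol 7.3 gives the Week 52 visit a window of 2 weeks either side. SAP 1.2 repeats that tolerance for the 13-weekly visits.

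**The concern.** A row called Week 52 is normally read as the state after about a year of treatment. Under this rule it would also hold records from women whose treatment ended earlier, by an amount the SAP does not state. Protocol 5.4 also calls for final evaluations when study drug is stopped. EOS records may therefore include individual withdrawals at any week, some of them sampled after the last dose; the SAP does not say.

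For measures with an earlier scheduled visit, the reader still has at least one row at a known time. For CTx and BSAP there is none: the change from baseline in that row is the whole blinded-phase summary of the endpoint. PK/PD results are one of the two things the shortened report is meant to deliver, so the time attached to them matters even though everything is descriptive.

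**Working it through.** The documents give no figure for this rule, so there is none to reproduce. The check is a count from the visit schedule.

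**Inputs.** Protocol Appendix 1, supported by the Synopsis (safety measures) and sections 7.3, 8.6 and 8.7, for scheduled blinded-phase post-baseline assessments. SAP 3.7 for the blinded visits (Weeks 13, 26, 39, 52). Protocol 7.3 for the window: 52 - 2 = 50 to 52 + 2 = 54 weeks.

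**Step 1. Visits left unmixed = scheduled post-baseline visits minus the pooled Week 52.**

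| Measure | Scheduled weeks | Count | Left unmixed |
|---|---|---|---|
| Vital signs | 13, 26, 39, 52 | 4 | 4 - 1 = 3 |
| PK (E and Z isomers) | 13, 26, 52 | 3 | 3 - 1 = 2 |
| Hematology and chemistry (incl. lipids) | 26, 52 | 2 | 2 - 1 = 1 |
| Coagulation | 26, 52 | 2 | 2 - 1 = 1 |
| CTx and BSAP | 52 | 1 | 1 - 1 = 0 |
| FSH, estradiol, estrone | 52 | 1 | 1 - 1 = 0 |
| SHBG | 52 | 1 | 1 - 1 = 0 |
| Physical examination | 52 | 1 | 1 - 1 = 0 |

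Every measure with a zero also has a screening or pre-dose value. The gap is in post-baseline rows only.

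**Step 2. Which zeros lead to a by-visit summary stated in the SAP.** SAP 3.6 names by-visit summaries for CTx/BSAP and for FSH, estradiol and estrone. It names none for SHBG. SAP 3.3.1 summarizes physical examination as abnormalities. Only CTx/BSAP is both a listed endpoint (SAP 2.2.2, item 7) and confirmed as a by-visit summary with nothing left unmixed.

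**Step 3. Can the time mix be recovered from the planned tables?** The eight subject-information tables in SAP 4.1.1 include drug compliance by visit but no duration-of-exposure table. No table title in SAP 4.1 offers weeks on treatment at the EOS record.

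**Step 4. What the label could hide (assumed inputs, illustration only).** Let f be the share of EOS records in the row, all taken at week w, with the rest at 52. Mean time in the row = (1 - f) x 52 + f x w.

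- f = 25%, w = 39: 39 + 9.75 = 48.75 weeks
- f = 50%, w = 26: 26 + 13 = 39 weeks
- f = 75%, w = 13: 13 + 9.75 = 22.75 weeks

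The documents give neither f nor w. This shows how far the time label could drift, not how far a marker value would.

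**The case against.** The strongest reply is that the plan is open about this. The pooling is disclosed in a section on changes, the visit is called nominal, SAP 1.3 states that exposure was shorter and promises cautious, descriptive reading, and SAP 4.2 plans individual listings of bone markers, hormones and discontinued subjects. Pooling also keeps every final record in view. The table shells are not visible here, so the printed row may already carry a Week 52/EOS label.

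Much of that stands, and it lowers the severity. The supportable claim is only that the SAP text states no window and no separate row; how the tables will be labeled cannot be checked. It does not remove the point. Cautious reading needs the time mix, which no titled summary table offers, and a listing does not correct a summary row. Separating the rows loses no record.

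Three wider readings are tempting, and the documents do not carry them:

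- **Physical examination is hit as hard as the bone markers.** It also has only Week 52, but it is summarized as abnormalities rather than mean change, and under Protocol 8.6 post-dose findings that qualify as adverse events go to the AE form.
- **SHBG is a second endpoint with the same fault.** That holds only if SHBG is tabulated, and SAP 3.6 names no summary of it. If it is not tabulated, the fault is omission, a different matter.
- **Week 104 records could enter the row.** The protocol does call both Week 52 and Week 104 an End of Study visit. But the rule follows a sentence about the missed end of the blinded phase, PK/PD reporting is limited to that phase, and the table titles say so. This needs a word of clarification at most.

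**Conclusion.** The point holds as a reporting fault. Followed as written, SAP 3.8 produces a nominal Week 52 summary of unstated mixed exposure. For CTx/BSAP, and less importantly for FSH, estradiol and estrone, no other blinded-phase post-baseline visit is scheduled to set beside it. This rests on the schedule in Appendix 1 and on the SAP's own statements about missed visits and shorter treatment.

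The effect on the marker values cannot be computed. A reader might infer that the 52-week change is diluted by some percentage. That would need the share of EOS records, their timing and a linear change over time, none of which the documents give. The row could understate a change that builds up, overstate a transient one, or be unaffected if the marker plateaus early.

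A reader might also infer a bias between arms. Both arms are pooled the same way, and the sponsor's decision to terminate is not tied to arm, so the documents give no reason to expect one to be favored. Nor is a primary test affected: SAP 3.3.2 plans no efficacy analysis for the report. Adverse event incidence does not depend on the rule.

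Severity: minor to moderate.

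**What to change.** Amend SAP 3.8 for the blinded-phase by-visit tables:

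1. Show a Week 52 row limited to records within the protocol window (52 +/- 2 weeks, that is 50 to 54), whether entered as Week 52 or as EOS.
2. Put all other blinded-phase final records in a separate row, 'EOS/out of window', by arm, with a summary of weeks since first dose and days since last dose. This row takes both EOS records and scheduled Week 52 visits that fell outside the window, so that a visit at week 49 or 55, for example, is not lost between rows.
3. If a pooled row is kept, label it 'Week 52/EOS (last value)' and show it beside the Week 52-only row.

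The cost is visit-window programming, one extra row per table and a smaller n at Week 52. No new data are needed: Protocol 5.4 already requires the date of stopping study drug in the CRF.

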	15. Women with a concurrent illness, disease or condition that, in the
	opinion of the Investigator, would limit their compliance with
	study requirements or place them at additional risk.

Test Product, Dose, and Mode of Administration:	The BHR-700 gel formulation contains 2 mg/mL 4-OH tamoxifen (0.2%) in a clear, colorless, absorptive hydro-alcoholic gel base formulated to provide continuous release of 4-OH tamoxifen. The BHR-700 gel is supplied in a non-aerosol canister with a 1 mL fixed-dose pump.
	Two (2) fixed unit doses of BHR-700 gel will be applied daily to each breast. Each actuation dispenses 1 mL of gel. A total of 8 mg/day (4 mg/breast) of 4-OHT will be administered daily, unless dose reduction by the Investigator, is deemed necessary for reasons of tolerability.
	The placebo gel is identical in appearance and consistency to the BHR-700 gel.
	Treatment compliance will be monitored by the Investigator staff who will check subject diaries and weigh the IP canister(s) when dispensed and upon return.
Duration of Treatment:	Up to 52 weeks for primary efficacy assessment with an optional and additional 52 weeks of open-label treatment of BHR-700 gel.
Criteria for Evaluation	
Efficacy Measures:	Mammograms will be centrally analyzed. The reader will be blinded as to the treatment group (BHR-700 gel or placebo) and time point of each subject. Cumulus 2D will be the primary endpoint method with Volpara 3D as a secondary endpoint method.
Safety Measures:	
 
Safety assessments will include evaluation of all AEs/serious adverse events (SAEs), with special attention given to uterine abnormalities, cardiovascular events, and thromboembolic events. Additional important safety parameters specific for this indication are: 
 
Endometrial changes
 
Breast evaluation
 
Coagulation factors
 
Bone biomarkers
 
Changes in menstrual cycle; unexpected vaginal bleeding
 
 
 

	To address these safety parameters, subjects will undergo the following assessments:
	A bilateral mammogram with both the raw and processed 2D image DICOM files needs to be performed within 3 months prior to randomization. The same (make/model/serial number) mammography machine must be used for the Week 52 mammogram, and if the subject is participating in the Open-Label phase, the Week 104 mammogram. If the mammogram is older than 3 months but less than 18 months, or it cannot be provided in the format required for

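### SAP 2.2.2 sets coagulation, bone-marker, SHBG and plasma 4-OHT endpoints for both phases, but SAP 3.8 and Section 5 plan no open-label output for them

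*SAP*

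**What the plan says.** SAP 2.2.2 lists ten secondary endpoints. They include changes in SHBG (item 5) and in four coagulation parameters (item 6), "Change in serum concentration of select bone biomarkers CTx and BSAP" (item 7), and "Pharmacokinetic (PK) plasma concentration of the E and Z isomers of 4-OHT after 13, 26, 52, 78, and 104 weeks" (item 10). The section closes: "The secondary endpoints are for both blind and open-label treatment phases".

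SAP 3.8, which records changes made because of early termination, says the report "will focus on the safety and PK/PD results, where PK/PD results of blind phase will be reported only". The output lists follow 3.8. Hormone, bone-marker, coagulation, plasma and endometrial outputs appear in 4.1.3 and 4.2.3 for the blinded phase. Section 5 has no counterpart; its open-label outputs cover subject information, adverse events, vital signs, physical examination, hematology, blood chemistry and pregnancy tests.

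The protocol synopsis, under Safety Measures, gives a list introduced by "Additional important safety parameters specific for this indication are". Endometrial changes, coagulation factors and bone biomarkers are on it. Protocol 7.4 and Appendix 1 schedule coagulation and PK at Weeks 78 and 104, and bone markers and SHBG at Week 104. Protocol 9.3 plans a further analysis once the last subject leaves the open-label phase.

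On the form of the summaries, SAP 3.6 specifies level and change from baseline for bone markers. Coagulation parameters "will be summarized by visit and treatment group. Individual data listing will be provided as well", with no mention of change. The hormones named in 3.6 are FSH, estradiol and estrone; SHBG is not among them, although SAP 3.7 lists it under hormones.

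**The concern.** After early termination the report is essentially a safety report, so what it leaves out matters. The restriction follows the PK/PD label rather than the role of the data. Coagulation is drawn at the same Week 78 and Week 104 visits as hematology and chemistry, yet only the latter two reach the open-label outputs.

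Two groups are affected. Women first randomised to placebo receive BHR-700 only in the extension, so for those who entered it, every on-drug value of these parameters falls in the unreported period. For women on active drug from the start, exposure beyond the blinded phase has no planned laboratory summary for these parameters. The protocol's rationale section describes earlier experience at doses up to 4 mg/day, against 8 mg/day here, and the protocol gives thromboembolic events special attention. Longer-exposure coagulation values are thus among the data a safety reader would look for.

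**Working it through.** The documents state no total or share of draws, so there is no plan figure to reproduce. The check counts scheduled draws and matches them to the planned outputs.

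**Scheduled post-baseline draws** (Protocol 7.3, 7.4 and Appendix 1) against SAP Sections 4 and 5:

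| Parameter | Blinded phase | Open-label phase | Open-label output in Section 5 | Share without output |
|---|---|---|---|---|
| Coagulation | Weeks 26, 52 | Weeks 78, 104 | none | 2/4 = 50% |
| Bone markers | Week 52 | Week 104 | none | 1/2 = 50% |
| SHBG | Week 52 | Week 104 | none | 1/2 = 50% |
| Plasma 4-OHT | Weeks 13, 26, 52 | Weeks 78, 104 | none | 2/5 = 40% |
| Hematology, chemistry | Weeks 26, 52 | Weeks 78, 104 | tables and listings | 0 |

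These shares apply to a woman who completes both phases.

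**Allowing for the optional extension.** Let p be the fraction of blinded-phase completers who enter and complete the extension. The documents do not give p, so it is an assumption shown as a range.

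- Coagulation: 2p/(2 + 2p) = p/(1 + p)
- Bone markers and SHBG: p/(1 + p)
- Plasma 4-OHT: 2p/(3 + 2p)

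| p | Coagulation, bone markers, SHBG | Plasma 4-OHT |
|---|---|---|
| 1 | 50% | 40% |
| 0.75 | 43% | 33% |
| 0.5 | 33% | 25% |
| 0.25 | 20% | 14% |

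Women who left during the blinded phase after giving some samples add to the denominator only. For parameters drawn before Week 52 this lowers the shares further.

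**Former placebo women.** All extension treatment is BHR-700, so their on-drug draws are those at Weeks 78 and 104 (Week 104 only for bone markers and SHBG). None has a planned output: for these women the share of on-drug values without output is 100%, whatever p is.

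**Baseline.** SAP 3.7 sets one baseline, at or before the first dose, for both phases. For a former placebo woman, change from that baseline at Week 78 or 104 spans the placebo year as well as the time on drug. Any open-label summary of change therefore needs a second reference value.

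**The case against.** The strongest reply is that this is a declared change. It stands in the section reserved for changes to the planned analysis, with early termination as the reason, and Section 5 follows it consistently. Section 2 of the SAP merely restates the planned endpoints: it also keeps the primary endpoint although 3.3.2 drops the efficacy analysis. On this view only a tidying of 2.2.2 remains. It is true that nothing is hidden. But early termination does not explain why open-label chemistry is reported and coagulation from the same visit is not. The precedence rule in Protocol 9.1 settles conflicts between protocol and SAP, not a conflict within the SAP.

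A second reply is that safety signals would surface elsewhere: clinically significant laboratory changes can be recorded as adverse events, which have open-label tables, and an unblinded DSMB reviews plasma 4-OHT and adverse events. This reduces the risk but does not replace the summaries. Under Protocol 8.2 a laboratory change may become an adverse event only if judged clinically significant, so a modest shift in group means would not appear.

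Several stronger readings are tempting but unsupported:

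- *Half of all coagulation draws are lost, affecting up to 110 placebo women (330 × 1/3).* Both are ceilings from the schedule. The plan itself expected only 91 evaluable placebo women, the extension is optional, and SAP 3.8 says many women had no Week 52 visit.
- *The data will never be reported.* The documents show only that no output is planned for the study report.
- *Endometrial change is an endpoint dropped in the same way.* It is not an endpoint in 2.2.2, and uterine events fall under adverse events. The case for listing it rests on the protocol's safety list.
- *Coagulation will be shown by level alone.* The wording of 3.6 suggests this, but the table shells are not available to confirm it.
- *SHBG is securely reported for the blinded phase.* This is only implied, by the hormone table and the laboratory list in 3.7.

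**Conclusion.** The contradiction is real. SAP 2.2.2 assigns these four sets of endpoints to both phases, while 3.8 and Section 5 confine them to the blinded phase without a reason that fits the rest of the open-label reporting. For a woman completing both phases, the scheduled draws left out are 2 of 4 for coagulation, 1 of 2 each for bone markers and SHBG, and 2 of 5 for plasma 4-OHT. These are upper bounds for the trial as a whole; the actual share depends on extension entry and completion, which the documents do not give, and is probably lower. The firmest consequence does not depend on those numbers: former placebo women in the extension would contribute no on-drug values for these parameters to the planned report. The point should be corrected because the data are scheduled for collection and the remedy is cheap. It concerns the completeness of the safety report, not the validity of the blinded comparison.

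**What to change.** In SAP 3.8, delete the clause restricting PK/PD reporting to the blinded phase. In Section 5, add open-label summaries, or at minimum listings, of coagulation, bone markers, hormones including SHBG, and plasma 4-OHT, split by original arm. For former placebo women, also show change from the last value before open-label dosing for coagulation, bone markers and SHBG. Add endometrial results to the open-label listings if any exist, citing the protocol's safety list rather than 2.2.2.

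In SAP 3.6, state that coagulation is summarised as level and change from baseline, to match endpoint 6, and name SHBG among the hormones.

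If the sponsor prefers to keep the restriction, 2.2.2 should be amended to match and a reason given that explains why open-label hematology and chemistry are treated differently. That would remove the contradiction but leave the gap in the safety report.

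The cost is SAP wording and a re-run of already planned programs on collected data, plus the added reference value for former placebo women. The downside is a few more pages in a brief report, with small numbers at Weeks 78 and 104 that allow description only.
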